Counts reflect numbers of subjects reporting one or more TEAE that map to the MedDRA system organ class/preferred term. At each level of summarization (system organ class or preferred term), subjects reporting more than one TEAE are counted only once under the earliest Study Day when the event of greatest severity was reported.

Source: Listing 16.2.7

O:\Studies\EmitBio\EB-P12-01\Biometrics\Programs\Tables\xxx.sas ran on Month Day, Year at hh:mm on data from Month Day, Year.

Table 14.3.2 – Reactogenicity by Visit for Safety Population

Study Visit	Category	4 Days RD-X19 n (%)	7 Days RD-X19 n (%)	Sham n (%)
Visit 1 /Day 1	N	XX	XX	XX
	n (%) subject with illumination site pain	XX (XX.X)	XX (XX.X)	XX (XX.X)
	n (%) subject with illumination site erythema	XX (XX.X)	XX (XX.X)	XX (XX.X)
	n (%) subject with illumination site Edema/Induration	XX (XX.X)	XX (XX.X)	XX (XX.X)
	n (%) subject with other pain, redness, swelling, or lesion of the oral mucosa	XX (XX.X)	XX (XX.X)	XX (XX.X)
Visit 2 /Day 2	N	XX	XX	XX
	n (%) subject with illumination site pain	XX (XX.X)	XX (XX.X)	XX (XX.X)
	n (%) subject with illumination site erythema	XX (XX.X)	XX (XX.X)	XX (XX.X)
	n (%) subject with illumination site Edema/Induration	XX (XX.X)	XX (XX.X)	XX (XX.X)
	n (%) subject with other pain, redness, swelling, or lesion of the oral mucosa	XX (XX.X)	XX (XX.X)	XX (XX.X)
Visit 3 /Day 3	...			
Visit 4 /Day 5	...			
Visit 5 /Day 8/ET	...			

Source: Listing 16.2.9.1

O:\Studies\EmitBio\EB-P12-01\Biometrics\Programs\Tables\xxx.sas ran on Month Day, Year at hh:mm on data from Month Day, Year.

Table 14.3.3 – Oropharyngeal Assessment by Visit for Safety Population

Study Visit	Category	4 Days RD-X19 n (%)	7 Days RD-X19 n (%)	Sham n (%)
Overall*	N	XX	XX	XX
	Normal	XX (XX.X)	XX (XX.X)	XX (XX.X)
	Abnormal	XX (XX.X)	XX (XX.X)	XX (XX.X)
Visit 1 /Day 1	N	XX	XX	XX
	Normal	XX (XX.X)	XX (XX.X)	XX (XX.X)
	Abnormal	XX (XX.X)	XX (XX.X)	XX (XX.X)
Visit 2 /Day 2	N	XX	XX	XX
	Normal	XX (XX.X)	XX (XX.X)	XX (XX.X)
	Abnormal	XX (XX.X)	XX (XX.X)	XX (XX.X)
Visit 3 /Day 3	...			
Visit 4 /Day 5	...			
Visit 5 /Day 8/ET	...			

*For Overall, Normal category includes subjects with a normal result for all visits; Abnormal category includes subjects with an abnormal result at any visit.

Source: Listing 16.2.9.2

O:\Studies\EmitBio\EB-P12-01\Biometrics\Programs\Tables\xxx.sas ran on Month Day, Year at hh:mm on data from Month Day, Year.

Table 14.3.4 – Vital Signs by Visit for Safety Population

Vital Sign	Study Visit	Category	Statistics	4 Days RD-X19 (N=XX)	7 Days RD-X19 (N=XX)	Sham (N=XX)	
Systolic Blood Pressure (mmHg)	Visit 1 /Day 1 (Baseline)	Actual Value	N	XX	XX	XX	
			Mean \pm SD	XX.X \pm XX.X	XX.X \pm XX.X	XX.X \pm XX.X	
			Median	XX.X	XX.X	XX.X	
			Min, Max	XX, XX	XX, XX	XX, XX	
		Actual Value	N	XX	XX	XX	
	Visit 5 /Day 8/ET		Mean \pm SD	XX.X \pm XX.X	XX.X \pm XX.X	XX.X \pm XX.X	
			Median	XX.X	XX.X	XX.X	
			Min, Max	XX, XX	XX, XX	XX, XX	
	Change from Baseline	Mean \pm SD	XX.X \pm XX.X	XX.X \pm XX.X	XX.X \pm XX.X		
		Median	XX.X	XX.X	XX.X		
		Min, Max	XX, XX	XX, XX	XX, XX		
Diastolic Blood Pressure (mmHg)	...						
Heart Rate (beats/min)	...						
Temperature (F)	...						
Respiratory (breaths/min)	...						

Source: Listing 16.2.9.3

O:\Studies\ EmitBio\EB-P12-01\Biometrics\Programs\Tables\xxx.sas ran on Month Day, Year at hh:mm on data from Month Day, Year

Table 14.3.5 – Methemoglobin by Visit for Safety Population

Study Visit	Category	Statistics	4 Days RD-X19 (N=XX)	7 Days RD-X19 (N=XX)	Sham (N=XX)
Visit 1 /Day 1 (Baseline)	Actual Value	N	XX	XX	XX
		Mean ± SD	XX.X ± XX.X	XX.X ± XX.X	XX.X ± XX.X
		Median	XX.X	XX.X	XX.X
		Min, Max	XX, XX	XX, XX	XX, XX
Visit 5 /Day 8/ET	Actual Value	N	XX	XX	XX
		Mean ± SD	XX.X ± XX.X	XX.X ± XX.X	XX.X ± XX.X
		Median	XX.X	XX.X	XX.X
		Min, Max	XX, XX	XX, XX	XX, XX
	Change from Baseline	Mean ± SD	XX.X ± XX.X	XX.X ± XX.X	XX.X ± XX.X
		Median	XX.X	XX.X	XX.X
		Min, Max	XX, XX	XX, XX	XX, XX

Source: Listing 16.2.9.6

O:\Studies\ EmitBio\EB-P12-01\Biometrics\Programs\Tables\xxx.sas ran on Month Day, Year at hh:mm on data from Month Day, Year

Data Listings

Listing 16.2.1 - Subject Disposition

Subject	Cohort	Safety Population	ITT Population	PP Population	Date of First Treatment	Study Exit Date (Study Day)	Completed Study?	Primary Reason for Study Discontinuation
Treatment:								

Abbreviations: ITT, Intent-to-Treat; PP, Per-Protocol

Study Day is calculated relative to date of first treatment. Day 1 is the day of first treatment.

O:\Studies\ EmitBio\EB-P12-01\Biometrics\Programs\Listings\xxx.sas ran on Month Day, Year at hh:mm on data from Month Day, Year

Listing 16.2.2.1 - Protocol Deviations

Subject	Cohort	Major (Significant) Protocol Deviation?	Description of Deviation
Treatment:			

Major (Significant) protocol deviations are those that exclude subjects from the per-protocol analysis.

O:\Studies\ EmitBio\EB-P12-01\Biometrics\Programs\Listings\xxx.sas ran on Month Day, Year at hh:mm on data from Month Day, Year

Listing 16.2.2.2 - Informed Consent and Eligibility Criteria

Subject	Cohort	Date of Informed Consent	SARS-CoV-2 Rapid Antigen Test		Baseline/Randomization	
			Nasal swab collected and analyzed?	Result of Antigen Test	Subject met all Entry Criteria?	If No, Criterion Not Met

Treatment:

O:\Studies\ EmitBio\EB-P12-01\Biometrics\Programs\Listings\xxx.sas ran on Month Day, Year at hh:mm on data from Month Day, Year

Listing 16.2.2.3 - General Comments

Subject	Cohort	Date of Comment	eCRF Form/Module	Comment
Treatment:				

O:\Studies\ EmitBio\EB-P12-01\Biometrics\Programs\Listings\xxx.sas ran on Month Day, Year at hh:mm on data from Month Day, Year

Listing 16.2.4.1 - Demographics

Subject	Cohort	Date of Birth	Age	Sex	Ethnicity	Race
---------	--------	---------------	-----	-----	-----------	------

Treatment:

Age is calculated relative to date of informed consent.

O:\Studies\ EmitBio\EB-P12-01\Biometrics\Programs\Listings\xxx.sas ran on Month Day, Year at hh:mm on data from Month Day, Year

Listing 16.2.4.2 - Medical/Surgical History

Subject	Cohort	Subject had medical or surgical history?	Condition or Procedure	Onset Date	Stop Date	Concomitant medications?
Treatment:						

O:\Studies\ EmitBio\EB-P12-01\Biometrics\Programs\Listings\xxx.sas ran on Month Day, Year at hh:mm on data from Month Day, Year

Listing 16.2.5.1 - Subject Randomization, Dosing Diary and Study Device Dispensing at Visit 1/Day 1, and Illumination Treatment at Site

Subject	Cohort	Randomization Number	Date of Randomization	Dosing instructions reviewed and dosing diary dispensed?	Investigational device dispensed to the subject?	Initials of Dispenser	Illumination treatment performed on site under supervision?		
							Visit 1 /Day 1	Visit 2 /Day 2	Visit 3 /Day 3
Treatment:									

O:\Studies\ EmitBio\EB-P12-01\Biometrics\Programs\Listings\xxx.sas ran on Month Day, Year at hh:mm on data from Month Day, Year

Listing 16.2.5.2 – Treatment Record and Subject Diary Collection at End of Study

Subject	Cohort	Subject applied at least one treatment?	Total Illumination Treatments	Total Treatments Missed	Subject diary collected?	Investigational device collected?	Initials of Collector
Treatment:							

O:\Studies\ EmitBio\EB-P12-01\Biometrics\Programs\Listings\xxx.sas ran on Month Day, Year at hh:mm on data from Month Day, Year

Listing 16.2.5.3 – Treatment Application Log

Subject	Cohort	Dose Number	Date of Dose	Time of Dose	Missed Dose	Dose Not Applicable	Unknown
Treatment:							

O:\Studies\ EmitBio\EB-P12-01\Biometrics\Programs\Listings\xxx.sas ran on Month Day, Year at hh:mm on data from Month Day, Year

Listing 16.2.6.1.1 – COVID-19 Symptom Assessment and Severity Score

Subject	Cohort	Visit	Assessment		Sore Throat	Nasal Congestion	Headache	Chills/ Sweats	Muscle or Joint pain	Fatigue	Nausea	Fever (F)	COVID-19 Severity Score
			Study Day	Date:Time									
Treatment:													

COVID-19 Symptom: 0=None, 1=Mild, 2=Moderate, 3=Severe. Study Day is calculated relative to date of first treatment. Day 1 is the day of first treatment.

Note: Assessment at a visit was based on symptoms the subject reports as occurring within the past 3 days of that visit.

O:\Studies\ EmitBio\EB-P12-01\Biometrics\Programs\Listings\xxx.sas ran on Month Day, Year at hh:mm on data from Month Day, Year

Listing 16.2.6.1.2- COVID-19 Symptom Assessment and Severity Score from Subject Diary

Site-Subject	Cohort	Not Done	Day	Assessment										COVID-19 Severity Score
				Study Day	Date:Time	Cough	Sore Throat	Nasal Congestion	Headache	Chills/ Sweats	Muscle or Joint pain	Fatigue	Nausea	
Treatment:														
xxxx	x	Day 1- Assessment 1	1											
		Day 1- Assessment 2	1											
		Day 2- Assessment 1	2											

COVID-19 Symptom: 0=None, 1=Mild, 2=Moderate, 3=Severe. Study Day is calculated relative to date of first treatment. Day 1 is the day of first treatment.

Note: Assessment at a visit was based on symptoms the subject reports as occurring within the past 3 days of that visit.

O:\Studies\ EmitBio\EB-P12-01\Biometrics\Programs\Listings\xxx.sas ran on Month Day, Year at hh:mm on data from Month Day, Year

Listing 16.2.6.2 – Clearance of COVID-19 Symptoms

Subject	Cohort	Has there been a timepoint/day that ALL of the subject's Covid-19 symptom assessment scores reached 0 and/or 1?	Date (Study Day)	Time
Treatment:				

Study Day is calculated relative to date of first treatment. Day 1 is the day of first treatment.

O:\Studies\ EmitBio\EB-P12-01\Biometrics\Programs\Listings\xxx.sas ran on Month Day, Year at hh:mm on data from Month Day, Year

Listing 16.2.6.3 – Viral Load via Saliva Specimen and Oropharyngeal Swab Collection

Subject	Cohort	Type of Biospecimen	Visit	Sample Received		Test Date (Study Day)	Test Result	Average N1 Ct	RP Ct	Viral Load Quantitation (copies/mL)
				Date (Study Day)	Time					
Treatment:										

Study Day is calculated relative to date of first treatment. Day 1 is the day of first treatment.

O:\Studies\ EmitBio\EB-P12-01\Biometrics\Programs\Listings\xxx.sas ran on Month Day, Year at hh:mm on data from Month Day, Year

Listing 16.2.6.4 – Derived Clearance of Viral Infection and Time-Weighted Average Change from Baseline in Log10-Transformed Viral Load via RT-qPCR

Subject	Cohort	Analysis	Clearance of Viral Infection (Study Day)				Change from Baseline in Log10-Transformed Viral Load (Study Day)			TWA Change from Day 1 to Day 8
			Visit 2 /Day 2	Visit 3 /Day 3	Visit 4 /Day 5	Visit 5 /Day 8	Visit 3 /Day 3	Visit 4 /Day 5	Visit 5 /Day 8	
Treatment:										
	ITT		No (2)	No (3)	No (5)	No (9)	xx.x (3)	xx.x (5)	xx.x (9)	xx.x
	PP		No (2)	No (3)		No (9)	xx.x (3)		xx.x (9)	xx.x

Abbreviation: ITT = Intent-to-Treat, PP = Per-Protocol, TWA = Time-Weighted Average, LOCF = Last observation carried forward
Study Day is calculated relative to date of first treatment. Day 1 is the day of first treatment.

For the ITT analysis, missing viral load will be imputed using the LOCF method.

Note 1: Clearance of viral infection is defined, based on viral load via RT-qPCR, as achievement of: [1] RP Ct ≥ 0 , AND [2] Average N1 Ct ≥ 32 or Average N1 Ct = “Undetermined”.

Note 2: TWA Change from Day 1 to Day 8 is calculated using the trapezoidal rule.

O:\Studies\ EmitBio\EB-P12-01\Biometrics\Programs\Listings\xxx.sas ran on Month Day, Year at hh:mm on data from Month Day, Year

Listing 16.2.7 - Adverse Events

Subject	Cohort	AE No.	System Organ Class / Preferred Term / Event Name	Occurred prior to first dose?	Start Date (Study Day)	Stop Date (Study Day)	Serious AE?	Intensity	Causality to Study Device	Action Taken	Outcome
Treatment:											

Note: Adverse events coded in MedDRA, version xx.x

Study Day is calculated relative to date of first treatment. Day 1 is the day of first treatment while Day -1 is the day prior to first treatment.

O:\Studies\EmitBio\EB-P12-01\Biometrics\Programs\Listings\xxx.sas ran on Month Day, Year at hh:mm on data from Month Day, Year

Listing 16.2.8.1 – Out-of-Range Results of Clinical Laboratory Tests

Subject	Cohort	Visit	Lab Panel	Test Name	Result	Flag	Out of Range: NCS or CS
---------	--------	-------	-----------	-----------	--------	------	-------------------------

Treatment:

Abbreviation: CS = clinically significant, NCS = not clinically significant

O:\Studies\ EmitBio\EB-P12-01\Biometrics\Programs\Listings\xxx.sas ran on Month Day, Year at hh:mm on data from Month Day, Year

Listing 16.2.8.2 - Pregnancy Test (Female Subjects Only)

Subject	Cohort	Visit	Pregnancy Test Done?	If not done, subject is not of childbearing potential due to	Date of Test (Study Day)	Result
Treatment:						

Study Day is calculated relative to date of first treatment. Day 1 is the day of first treatment.

O:\Studies\ EmitBio\EB-P12-01\Biometrics\Programs\Listings\xxx.sas ran on Month Day, Year at hh:mm on data from Month Day, Year

Listing 16.2.9.1 - Reactogenicity Assessment

Subject	Cohort	Visit	Illumination Site Pain?	Illumination Site Erythema?	Illumination Site Edema/ Induration?	Other pain, redness, swelling, or lesion of the oral mucosa?
Treatment:						

O:\Studies\ EmitBio\EB-P12-01\Biometrics\Programs\Listings\xxx.sas ran on Month Day, Year at hh:mm on data from Month Day, Year

Listing 16.2.9.2 - Oropharyngeal Assessment

Subject	Cohort	Visit	Oropharyngeal Assessment performed?	Any changes since previous visit?	Assessment Result	Description of Abnormality
Treatment:						

O:\Studies\ EmitBio\EB-P12-01\Biometrics\Programs\Listings\xxx.sas ran on Month Day, Year at hh:mm on data from Month Day, Year

Listing 16.2.9.3 - Vital Signs

Subject Cohort	Visit	Height (in)	Weight (lb)	Body Mass Index (kg/m ²)	Systolic Blood Pressure (mmHg)	Diastolic Blood Pressure (mmHg)	Heart Rate (beats/min)	Respiratory Rate (breaths/min)	Temperature (F)
Treatment:								XX /NCS	XXX /NCS

For out-of-range results, CS = clinically significant, NCS = not clinically significant.

O:\Studies\ EmitBio\EB-P12-01\Biometrics\Programs\Listings\xxx.sas ran on Month Day, Year at hh:mm on data from Month Day, Year

Listing 16.2.9.4 - Physical Examination

Subject	Cohort	Visit	PE Performed?	Subject requires a targeted PE?	Test Name	Description of Abnormality
Treatment:						

O:\Studies\ EmitBio\EB-P12-01\Biometrics\Programs\Listings\xxx.sas ran on Month Day, Year at hh:mm on data from Month Day, Year

Listing 16.2.9.5 - Prior and Concomitant Medications

Subject	Cohort	WHO Class / WHO Drug Name / Medication Name	Start Date (Study Day)	End Date (Study Day)	Dose	Unit	Route	Frequency	Indication
Treatment:									

Abbreviations: ATC = anatomic therapeutic chemical; WHODDE, World Health Organization Drug Dictionary Enhanced
Medications are coded to ATC class and drug names using the WHODDE, version xxxx.

Study Day is calculated relative to date of first treatment. Day 1 is the day of first treatment while Day -1 is the day prior to first treatment.
O:\Studies\ EmitBio\EB-P12-01\Biometrics\Programs\Listings\xxx.sas ran on Month Day, Year at hh:mm on data from Month Day, Year

Programming Note:

- *If specifications for indications are reported as an AE or MH #, merge with AE/MH data to present the actual reported event as the specification.*
- *When creating WHO Class, utilize ATC level 4 drug class; utilize level 3 term if level 4 is missing and level 2 if both level 3 and level 4 are missing in the dataset*

Listing 16.2.9.6 - Methemoglobin Measurement

Subject	Cohort	Visit	Methemoglobin measured?	Methemoglobin Result (Percent)
Treatment:				

O:\Studies\ EmitBio\EB-P12-01\Biometrics\Programs\Listings\xxx.sas ran on Month Day, Year at hh:mm on data from Month Day, Year

Statistical Analysis Plan Amendment #1

Protocol No.: EB-P12-01

Title: A Phase I/II Randomized, Dose Escalation Study to Evaluate the Safety and Antiviral Activity of the RD-X19 Device in SARS-CoV-2 Infected Individuals with Uncomplicated COVID-19

Previous SAP (v1.0) Date: December 17, 2020

Amendment 01 Date: January 25, 2021

Sponsor: EmitBio Inc.
[name]
[name]

Amendments:

Per sponsor request, diary of COVID-19 symptom assessments have been added to the database. Time to alleviation of COVID-19 symptoms should be derived based on the diary entries. Time to sustained alleviation is added to the list of secondary efficacy endpoints. For all time-to-event variables, Kaplan-Meier plots and log rank p-values for treatment comparisons will be provided. Content of interim analysis is adjusted.

1. Original Text and Location

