7.1 Inclusion Criteria

A subject must meet all the following criteria to be eligible to participate in this study:

1. Positive for SARS-CoV-2 antigen via nasal swab at or within the past 24 hours of the screening visit detected using an FDA authorized SARS-CoV-2 antigen test.
2. Onset of signs and symptoms consistent with COVID-19* no longer than within the past 3 days* and have either a) a fever of at least 100 °F or b) at least two moderate or severe

symptoms (cough, sore throat, nasal congestion, headache, chills/sweats, muscle or joint pain, fatigue, and nausea) at the time of screening.

3. Provides written informed consent prior to initiation of any study procedures.
4. Be able to understand and agrees to comply with planned study procedures and be available for all study visits.
5. Agrees to the collection of nasopharyngeal swabs, oropharyngeal swabs, oral saliva specimen collection and venous blood specimens per protocol.
6. Agrees to refrain from using oral antiseptics (e.g. hydrogen peroxide rinse, Listerine) or mouthwashes of any kind during the study.
7. Male or non-pregnant female, 18 to 65 years of age, inclusive, at time of enrollment.
8. No uncontrolled disease process (chronic or acute), other than COVID-19 signs and symptoms*.
9. No physical or mental conditions or attributes at the time of screening, which in the opinion of the PI, will prevent full adherence to, and completion of, the protocol.

*The following COVID-19 onset of signs and symptoms generally appear 2-7 days after exposure to SARS-CoV-2:

- Cough
- Sore Throat
- Nasal Congestion
- Headache
- Chills/sweats
- Muscle or joint pain
- Fatigue
- Nausea

Severity of COVID-19 symptoms will be assessed based on definitions used for graded adverse events:

- None (Grade 0): Not present
- Mild (Grade 1): Events that are usually transient and may require only minimal or no treatment or therapeutic intervention and generally do not interfere with the subject's usual activities of daily living.
- Moderate (Grade 2): Events that are usually alleviated with additional specific therapeutic intervention. The event interferes with usual activities of daily living causing discomfort but poses no significant or permanent risk of harm to the research subject.
- Severe (Grade 3): Events interrupt usual activities of daily living, or significantly affects clinical status, or may require intensive therapeutic intervention. Severe events are usually incapacitating.

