- Review all pre-study medications, vitamins, supplements, and therapies up to 14 days prior to the start of screening that could impact the use of, or response to, the device and record on the appropriate e-CRF. Subjects are allowed to use over-the-counter medications and remedies to alleviate symptoms (e.g. acetaminophen, ibuprofen, cough drops, etc. and should be recorded.)
- Measure vital signs (HR, BP, **RR**, and oral temperature) and height and weight for determination of BMI.
- Perform full physical examination which will include assessments of the following organs and organ systems: skin, head, ears, eyes, nose, and throat (HEENT), neck, lungs, heart, liver, spleen, abdomen, extremities, lymph nodes (axillary and cervical), and nervous system.
- Obtain blood and urine for clinical screening laboratory evaluations:
 - Comprehensive Metabolic Panel (fasting or non-fasting)
 - CBC with differential
 - Urine pregnancy test (in women of childbearing potential)
- Review inclusion and exclusion criteria.

The overall eligibility of the subject to participate in the study will be assessed once all screening values are available. The screening process can be suspended prior to complete assessment at any time if exclusions are identified by the study team.

Study subjects who qualify for inclusion will be immediately randomized for their day 1 visit.

If a physiologic parameter, e.g., vital signs, is outside of the protocol-specified range, then the measurement may be repeated once if, in the judgment of the participating clinical site PI or appropriate sub-investigator, the abnormality is the result of an acute, short-term, rapidly reversible condition (e.g., stress, anxiety or “white coat syndrome”) or other source of error. A physiologic parameter may also be repeated if there is a technical problem with the measurement caused by malfunctioning, or an inappropriate measuring device (i.e., inappropriate-sized BP cuff).

A subject may be re-screened if there is a transient disease status (e.g., absent signs and symptoms associated with mild COVID-19), or if a protocol eligibility criterion that is not met at the initial time of screening, will be met by rescreening of all assessments within the next 2 days using the same subject number.

No subjects may be screened more than twice due to a screening failure result as defined above.

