9.3 Efficacy Assessments

Efficacy comparisons will be made in the ITT Population with the intent of estimating the effect of the RD-X19 device relative to sham in several outcome measures. Subjects will be instructed to fill out diary cards twice daily to assess their symptoms associated with disease progression and record the number of treatments completed. Additionally, at Baseline and days 3, 5, and 8, subjects will provide two saliva specimens and an oropharyngeal swab for virology endpoint assessments. One saliva specimen will be collected, preserved, and shipped fresh to a central lab for assessment of SARS-CoV-2 mRNA via RT-qPCR. The second specimen and the oropharyngeal swab will be collected in separate collection tubes, frozen, and stored at the site and shipped to a central lab at the end of each cohort.

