3.2 Sample Size Determination

The study is hypothesis generating in nature. Hence, the sample size was selected for convenience.

The target number of subjects randomized is 60 in total, and 30 per cohort (20 subjects to RD-X19 and 10 subjects to sham).

4 Populations To Be Analyzed

Three subject populations are defined as follows:

- (1) Safety: This population will include all subjects who receive at least 1 study treatment. The Safety Population will be used for analysis of safety and tolerability data. Subjects will be analyzed based on actual treatment received.
- (2) Intent-to-Treat (ITT): This population will include all randomized subjects who receive treatment and were not discontinued due to a significant abnormality from the baseline CMP and CBC tests. This population will be used for all efficacy analyses as the primary population. Subjects will be analyzed based on randomized treatment, regardless of the actual treatment received.
- (3) Per-Protocol Population (PP): This population will include subjects who complete the study and did not have a major protocol deviation (MPD). The PP population will be used for supportive analysis of the efficacy endpoints. MPDs are those that could have interfered with the administration of treatment or the precise evaluation of treatment efficacy.

MPDs may include but will not be limited to the following:

- Violation of inclusion/exclusion criteria;
- Use of prohibited concomitant medications during the treatment period;
- No Day 3 Visit;

- Returned for Day 8 Visit outside the designated visit window;
- Was not compliant with the dosing regimen.

All MPDs will be identified before the database lock and study unblinding for analysis.

5 Planned Analyses

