5.5 Efficacy Variables and Analyses

All efficacy analyses will be performed for both the ITT and PP populations with results in ITT as primary and PP as supportive.

Viral load (log base 10 copies/mL) and cycle threshold (Ct) data that are continuous in nature but may be reported as “undetermined” or “inconclusive” or “<LOQ”. All virology data will be included in the efficacy analysis except the samples with “Inconclusive” viral load quantitation and the samples with an “Undetermined” RNase P (RP) internal control Ct value.

For analysis-qualified samples, results of “undetermined” and “<LOQ” will be handled as follows for data summary purpose:

- For viral load reported as “Undetermined”, value 1 will be used to calculate descriptive statistics. This will support the need for logarithm transformation.
- For viral load reported as “<LOQ”, value 5×10^1 will be used to calculate descriptive statistics.

In conjunction with above handling of the viral data scenarios, for purposes of this protocol, clearance of viral infection is defined as achievement of: [1] RP Ct ≥ 0 , AND [2] Average N1 Ct ≥ 32 or Average N1 Ct = “Undetermined”.

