5.5.2 Analysis of Secondary Efficacy Endpoints

The following 6 secondary efficacy endpoints will be summarized using descriptive statistics by visit, as appropriate:

- log10-transformed Viral load as measured in saliva by RT-qPCR at each visit by RT-qPCR
- proportion of subjects with $\geq 95\%$ reduction in SARS-CoV-2 viral load by RT-qPCR at each visit
- time to clearance of viral infection in saliva via RT-qPCR
- proportion of subjects demonstrating clearance of viral infection via RT-qPCR at Day 8/ET visit
- COVID-19 composite severity score at each visit
- time to alleviation of COVID-19 symptoms, defined as the number of hours from the first dose to the first time when all eight symptoms had been assessed by the subject as none (0) or mild (1)
- time to sustained alleviation of COVID-19 symptoms, defined the number of hours from the first dose to the time when all eight symptoms had been assessed by the subject as none (0) or mild (1) and no single symptom reoccurs later at a level above mild (1).

Both time to alleviation of COVID-19 symptoms and time to sustained alleviation of COVID-19 symptoms will be derived from self-assessment by study subjects and recorded on the subjects' diary cards.

For log10-transformed viral load data, geometric means will be computed by exponentiating (base 10) the group means of the log10-transformed viral load. Time-to-event variables will be evaluated using the Kaplan-Meier method and p-values for treatment comparison will be provided via log rank test.

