O:\Studies\EmitBio\EB-P12-01\Biometrics\Programs\Tables\xxx.sas ran on Month Day, Year at hh:mm on data from Month Day, Year.

Repeat Table 14.2.2.1 for the following:

Table 14.2.2.2 – Log10-Transformed Viral Load via RT-qPCR by Visit for Per-Protocol Population
 (with footnote 1 removed)

Table 14.2.2.3 – Proportion of Subjects with At Least 95% Reduction by Visit in SARS-CoV-2 Viral Load via RT-qPCR

Population	Study Visit	Statistics	4 Days RD-X19	7 Days RD-X19	Sham
Intent-to-Treat	Visit 3 /Day 3	N	XX	XX	XX
		n (%) Subjects with >=95% Reduction	XX (XX.X)	XX (XX.X)	XX (XX.X)
	Visit 4 /Day 5	N	XX	XX	XX
		n (%) Subjects with >=95% Reduction	XX (XX.X)	XX (XX.X)	XX (XX.X)
	Visit 5 /Day 8	N	XX	XX	XX
		n (%) Subjects with >=95% Reduction	XX (XX.X)	XX (XX.X)	XX (XX.X)
Per-Protocol	Visit 3 /Day 3	N	XX	XX	XX
		n (%) Subjects with >=95% Reduction	XX (XX.X)	XX (XX.X)	XX (XX.X)
	Visit 4 /Day 5	N	XX	XX	XX
		n (%) Subjects with >=95% Reduction	XX (XX.X)	XX (XX.X)	XX (XX.X)
	Visit 5 /Day 8	N	XX	XX	XX
		n (%) Subjects with >=95% Reduction	XX (XX.X)	XX (XX.X)	XX (XX.X)

Note: Missing data will be replaced for the efficacy endpoint in the ITT analyses using the Last observation carried forward (LOCF) method.

Source: Listing 16.2.6.3

O:\Studies\EmitBio\EB-P12-01\Biometrics\Programs\Tables\xxx.sas ran on Month Day, Year at hh:mm on data from Month Day, Year.

Table 14.2.3 – Clearance of Viral Infection in Saliva via RT-qPCR

Population	Endpoint	Statistics	4 Days RD-X19	7 Days RD-X19	Sham
Intent-to-Treat	Time to Clearance of Viral Infection	N	XX	XX	XX
		n (%) Censored	XX (XX.X)	XX (XX.X)	XX (XX.X)
		Median of Time	XX.X	XX.X	XX.X
		25 th , 75 th Percentiles	XX.X, XX.X	XX.X, XX.X	XX.X, XX.X
		95% CI of Median	(XX.X, XX.X)	(XX.X, XX.X)	(XX.X, XX.X)
		P-value RX-X19 vs. Sham	0.XXX	0.XXX	
	Subjects Demonstrating Clearance of Viral Infection at Day 8/ET Visit	n (%)	XX (XX.X)	XX (XX.X)	XX (XX.X)
Per-Protocol	Time to Clearance of Viral Infection	N	XX	XX	XX
		n (%) Censored	XX (XX.X)	XX (XX.X)	XX (XX.X)
		Median of Time	XX.X	XX.X	XX.X
		25 th , 75 th Percentiles	XX.X, XX.X	XX.X, XX.X	XX.X, XX.X
		95% CI of Median	(XX.X, XX.X)	(XX.X, XX.X)	(XX.X, XX.X)
		P-value RX-X19 vs. Sham	0.XXX	0.XXX	
	Subjects Demonstrating Clearance of Viral Infection at Day 8/ET Visit	(%)	XX (XX.X)	XX (XX.X)	XX (XX.X)

Abbreviation: CI = Confidence Interval

Subjects with clearance of viral infection at baseline are excluded from the analysis of time-to-clearance of viral infection.

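### Subjects already saliva-negative at baseline are excluded from time-to-clearance only, so Day 8 clearance and ≥95% reduction misclassify some of them

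*Combined protocol and SAP*

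**What the plan says.** **Entry.** The virological criterion in protocol 7.1 (version 2.0) is "Positive for SARS-CoV-2 antigen via nasal swab at or within the past 24 hours of the screening visit". No saliva or PCR result is required.

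**Measurement.** Protocol 9.3: "One saliva specimen will be collected, preserved, and shipped fresh to a central lab for assessment of SARS-CoV-2 mRNA via RT-qPCR". Protocol 9.1.1: "Study subjects who qualify for inclusion will be immediately randomized for their day 1 visit". The saliva result therefore comes back after randomisation and cannot decide who enters.

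**Analysis sets.** SAP section 4 says of the ITT set: "This population will be used for all efficacy analyses as the primary population". ITT removes only untreated subjects and those discontinued for a significant baseline CMP or CBC abnormality. The listed major deviations for the PP set do not include a negative baseline saliva PCR. SAP 5.5 drops only samples with inconclusive quantitation or an undetermined RNase P control, so a valid negative baseline sample is kept.

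**Values and definition.** For a viral load reported as Undetermined, SAP 5.5 states that "value 1 will be used to calculate descriptive statistics"; for <LOQ the value is 50. Clearance means a valid control with average N1 Ct of 32 or more, or Undetermined.

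**Baseline-negative rule.** The footnote to Table 14.2.3 reads "Subjects with clearance of viral infection at baseline are excluded from the analysis of time-to-clearance of viral infection". SAP 5.5.2 lists a separate endpoint, the "proportion of subjects demonstrating clearance of viral infection via RT-qPCR at Day 8/ET visit", with no such limit. Tables 14.2.2.3 (≥95% reduction) and 14.2.1.1 and 14.2.1.2 (TWA) have none either.

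**The concern.** The SAP foresees subjects who meet its clearance definition before treatment, but handles them for one endpoint only. Under the remaining rules the same subject can be a success on one secondary endpoint and an unavoidable failure on another, whatever the device does.

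The inconsistency is plainest inside Table 14.2.3. A subject removed from the time-to-clearance rows can reappear as cleared in the Day 8/ET row below. That row has no N of its own, so a reader cannot tell which denominator was used.

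The study is hypothesis-generating, so its effect estimates are its main product. Two of its response proportions would depend partly on how many subjects started without measurable saliva virus, and on how those subjects happened to fall between small arms.

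**Working it through.** **Inputs.** Substitution values 1 and 50 (SAP 5.5). Planned size 2 × (20 + 10) = 60, which agrees with SAP 3.2; Clarification Memorandum 2 allows up to 36 per cohort, which does not alter the point. The documents give no power calculation, expected clearance rate or baseline-negative share. Those figures below are assumptions.

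**1. ≥95% reduction, from the SAP's own values.** Reduction = 1 − later value / baseline value.
- Baseline Undetermined (1): the lowest later value is also 1, so the maximum reduction is 1 − 1/1 = 0%. The subject is a forced non-responder.
- Baseline <LOQ (50): a responder needs a later value of at most 0.05 × 50 = 2.5, so only a later Undetermined result qualifies. That gives 1 − 1/50 = 98%, a responder with no quantifiable virus at either visit.

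**2. Day 8 clearance.** Let f be the share cleared at baseline and still cleared at Day 8, equal in both arms, and p the clearance rate among the rest. The tabulated rate is f + (1 − f)p, so the arm difference is multiplied by (1 − f). With assumed rates of 40% and 20%:

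| f | Active | Sham | Difference |
|---|---|---|---|
| 0% | 40% | 20% | 20 points |
| 5% | 0.05 + 0.95 × 0.40 = 43% | 0.05 + 0.95 × 0.20 = 24% | 19 points |
| 10% | 0.10 + 0.90 × 0.40 = 46% | 0.10 + 0.90 × 0.20 = 28% | 18 points |
| 20% | 0.20 + 0.80 × 0.40 = 52% | 0.20 + 0.80 × 0.20 = 36% | 16 points |

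**3. Chance imbalance in one 20:10 cohort.** Suppose K of 30 subjects are baseline-negative. The hypergeometric probability that the arms differ by at least 15 points in baseline-negative share is 0.10, 0.53, 0.30 and 0.63 for K = 2, 3, 5 and 6. It jumps because the counts are so small. This bears on the Cohort 1 interim, where Table 14.2.2.3 compares about 20 with about 10 subjects.

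**4. Primary TWA.** From a baseline of 1 (log10 = 0) the change can only be zero or positive. From 50 (log10 = 1.70) it can fall by at most 1.70. A simulation of the SAP's ANCOVA gives an idea of scale: 4,000 runs; 20 per group with pooled sham; positive baselines with mean 6 and SD 1.2 log10; visit SD 1.2; baseline-negatives held at zero in every arm. The effect of −0.72 log10 with no baseline-negatives became −0.68, −0.66 and −0.59 at f = 5, 10 and 20%. Restricted to baseline-positives it stayed between −0.71 and −0.73. The dilution is partly built in, because the model gives baseline-negatives no treatment effect.

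**The case against.** Several counter-arguments are sound.

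- **Cleared is not the same as no virus.** Ct of 32 or more can include a quantifiable load. Such a subject can still show a ≥95% fall and a negative TWA change. A reader might infer that all baseline-cleared subjects carry no information. The documents do not support that: the floor is absolute only for Undetermined baselines. Even there, subjects enrol within three days of symptom onset, and a smaller rise on active than on sham would be informative. The Ct rule is therefore the wrong exclusion for the ≥95% endpoint.
- **Reversal by one or two subjects.** With only 10 sham subjects per cohort, a reader might infer that an imbalance of one or two could reverse the Day 8 comparison. It does not at 40% v 20%. With none cleared at baseline on active and two on sham, sham shows (2 + 18 × 0.2)/20 = 28%, or (2 + 8 × 0.2)/10 = 36% with a single cohort's sham. Both stay below 40%. Reversal would need 6 of 20 or 3 of 10. Table 14.2.3 is also not among the interim tables, and the final table has one pooled sham column.
- **The time-to-event exclusion is technical.** A subject negative at time zero has no time to clearance, so the exclusion need not carry over to a Day 8 status. That explains the footnote. It does not make clearance an apt label for someone who already met the definition.
- **ITT.** Keeping every treated randomised subject in the TWA model with baseline adjustment is defensible and follows the stated rule. This stands, and the primary analysis should not change.
- **Low stakes.** The two proportions are secondary, tabulated without p-values, in a study not powered for testing. This limits the severity. It does not remove the misclassification.

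Retention of these subjects is inferred from the population and sample rules; no sentence states it. SAP 5.5 gives the values 1 and 50 for summary purposes, and their use for responder status and TWA is assumed because no other rule appears.

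**Conclusion.** The point holds for the two secondary proportions. Following the stated rules, a subject cleared at baseline can count as cleared at Day 8 in the table that drops that subject from time-to-clearance. An Undetermined baseline is a forced failure for ≥95% reduction, and a <LOQ baseline can become a 98% responder without quantifiable virus at either visit. Those statements need only the SAP's own values, on the reading that the values apply to responder status.

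The size is uncertain and probably modest. At an assumed baseline-negative share of 5 to 20%, a 20-point clearance difference loses 1 to 4 points, provided those subjects stay cleared. The TWA attenuation also rests on an assumed share and on no effect in baseline-negatives, so it supports a supplementary table and no more. A reader might infer systematic bias, but baseline saliva status is measured before treatment, so the consequences are dilution and chance imbalance. The change should be made, but the primary analysis is not invalid without it.

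**What to change.** 1. **Table 14.2.3.** Compute the Day 8/ET clearance proportion among ITT (and PP) subjects who did not meet the clearance definition at baseline. Give the row its own N and show the number excluded per arm.
2. **Table 14.2.2.3.** Compute the ≥95% reduction proportion among subjects with a quantifiable baseline saliva load, that is, neither Undetermined nor <LOQ. Do not use the Ct ≥32 rule here. Show the number excluded per arm. Part of the floor remains: since 50/0.05 = 1,000, a <LOQ result is a response only from a baseline of at least 1,000 copies/mL. A footnote can say so.
3. **TWA.** Keep the full-ITT ANCOVA as primary, and add a supplementary table in subjects with a quantifiable baseline saliva load.

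Both restrictions use a pre-treatment measurement, so the randomised comparison is kept within each subset. The cost is SAP wording, two denominators and one additional table, with no new data or patients. The downside is a slightly smaller N in these tables. For the two secondary proportions it is also a departure from the rule in protocol 10.3 and SAP section 4 that ITT serves all efficacy analyses; the SAP should state this openly.
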